6.2.8 Dabrafenib +/- Trametinib Dose Modification for **Hypertension**

Increases in blood pressure (BP) have been observed in patients receiving trametinib. Recommendations for BP monitoring and

CONFIDENTIAL

This document is confidential. Do not disclose or use except as authorized.

management are provided below.

Monitoring: All BP assessments are to be performed as follows:

- In subjects with an initial BP reading within the hypertensive range, a second reading should be taken at least 1 minute later, with the two readings averaged to obtain a final BP measurement. The averaged value should be recorded in the eCRF.
- Visits to monitor increased blood pressure can be scheduled independently from the per-protocol visits outlined in the study calendar. Ideally, subsequent blood pressure assessments should be performed within 1 week.
- Persistent hypertension is defined as an increase of systolic BP (SBP) >140 mmHg and/or diastolic BP (DBP) >90 mmHg in three consecutive visits with blood pressure assessments from two readings.
- Asymptomatic hypertension is defined as an increase of SBP >140 mmHg and/or diastolic BP (DBP) >90 mmHg in the absence of headache, light-headedness, vertigo, tinnitus, episodes of fainting, or other symptoms indicative of hypertension.

CONFIDENTIAL

This document is confidential. Do not disclose or use except as authorized.

Table 6-7: Dabrafenib +/-or Trametinib Treatment Modification and Management Requirements for Hypertension

Event	Management Guideline	Dose Modification

(Scenario A)
 
 Asymptomatic and persistent^a SBP of ≥ 140 and < 160 mmHg, or DBP ≥ 90 and < 100 mmHg 
OR
 
 linically significant increase in DBP of 20 mmHg (but still below 100 mmHg) 	
 Adjust current or initiate new antihypertensive medication(s). Titrate antihypertensive medication(s) during the next 2 weeks to achieve well-controlled BP. If BP is not well-controlled within 2 weeks, consider referral to a specialist and go to scenario (B). 	
 Continue protocol therapy. If BP is not well-controlled within 2 weeks, consider referral to a specialist and go to scenario (B).

(Scenario B)
 
 Asymptomatic SBP ≥ 160 mmHg, or DBP ≥ 100 mmHg, 
OR
 
 Failure to achieve well-controlled BP within 2 weeks in Scenario A. 	
 Adjust current or initiate new antihypertensive medication(s). Titrate antihypertensive medication(s) during the next 2 weeks to achieve well-controlled BP. 	
 Interrupt trametinib if clinically indicated. Once BP is well-controlled, restart trametinib reduced by one dose level. Dabrafenib (if cohort 1) may be continued

(Scenario C)
 
 Symptomatic hypertension 
OR
 
 Persistent SBP ≥ 160 mmHg, or DBP ≥ 100 mmHg, despite antihypertensive medication and dose reduction of study treatment 	
 Adjust current or initiate new antihypertensive medication(s). Titrate antihypertensive medication(s) during the next 2 weeks to achieve well-controlled BP. Referral to a specialist for further evaluation and follow-up is recommended. 	
 Interrupt trametinib. Once BP is well controlled, restart trametinib reduced by one dose level. Dabrafenib (if cohort 1) may be continued.

(Scenario D)
 
Refractory hypertension unresponsive to above interventions or hypertensive crisis.
	
Continue follow-up per protocol.
	
 Discontinue trametinib. Hold dabrafenib until BP is controlled. If the treatment delay is > 21 days, overall PI should be consulted for resumption of dabrafenib.

CONFIDENTIAL

This document is confidential. Do not disclose or use except as authorized.

6.2.9 Dabrafenib +/-or Trametinib Dose Modification Requirements for **QTc Prolongation**

Table 6-8: Dabrafenib +/-or Trametinib Withholding and Stopping Criteria for QTc Prolongation

Prolongation	Action and Dose Modification

 • QTcB \geq501 msec, or • Uncorrected QT >600 msec, or • QTcB >530 msec for subjects with bundle branch block 	
 • Interrupt dabrafenib and trametinib (cohort 1) or trametinib (cohort 2) until QTcB prolongation resolves to grade 1 or baseline. • If the event resolves, restart dabrafenib and trametinib (cohort 1) or trametinib (cohort 2) treatment at current dose level. • If the event does not resolve, permanently discontinue dabrafenib and trametinib treatment. • If the event recurs, permanently discontinue study treatment.
Abbreviations: msec = milliseconds; QTcB = QT interval on electrocardiogram corrected using the Bazett's formula	

6.2.10 Dabrafenib +/-or Trametinib Dose Modification for **Diarrhea**

Episodes of diarrhea have been observed in patients receiving dabrafenib, trametinib, or both therapies in combination. Other, frequent causes for diarrhea including concomitant medications (*e.g.*, stool softeners, laxatives, antacids, *etc.*), infections caused by *C. difficile* or other pathogens, partial bowel obstruction, *etc.*, should be clinically excluded.

Table 6-9: Dabrafenib +/-or Trametinib Treatment Modification and Management Requirements for Diarrhea

CTCAE Grade	Management	Action and Dose Modification
-------------	------------	------------------------------

CONFIDENTIAL

This document is confidential. Do not disclose or use except as authorized.

Table 6-9: Dabrafenib +/- Trametinib Treatment Modification and Management Requirements for Diarrhea

CTCAE Grade	Management	Action and Dose Modification
Uncomplicated Diarrhea,¹ Grade 1 or 2	
 • Diet: Stop all lactose containing products; eat small meals, BRAT-diet (banana, rice, apples, toast) recommended. • Hydration: 8-10 large glasses of clear liquids per day (e.g., Gatorade or broth). • Loperamide³: Initially 4 mg, followed by 2 mg every 4 hours or after every unformed stool; maximum 16 mg/day. Continue until diarrhea-free for 12 hours. • Diarrhea >24 hours: Loperamide 2 mg every 2 hours; maximum 16 mg/day. Consider adding oral antibiotics. • Diarrhea >48 hours: Loperamide 2 mg every 2 hours; maximum 16 mg/day. Add budesonide or other second-line therapies (otretotide, or tincture of opium) and oral antibiotics. 	
 • Continue study treatment. • If diarrhea is grade 2 for > 48 hours, interrupt study treatment until diarrhea resolves to grade ≤1. • Restart study treatment at the same dose level.
Uncomplicated Diarrhea,¹ Grade 3 or 4 Any Complicated Diarrhea²	
 • Clinical evaluation mandatory. • Loperamide³: Initially 4 mg, followed by 2 mg every 4 hours or after every unformed stool; maximum 16 mg/day. Continue until diarrhea-free for 12 hours. • Oral antibiotics and second-line therapies if clinically indicated • Hydration: Intravenous fluids if clinically indicated. • Antibiotics (oral or intravenous) if clinically indicated. • Intervention should be continued until the subject is diarrhea-free for ≥24 hours. • Intervention may require hospitalization for subjects at risk of life-threatening complications. 	
 • Interrupt study treatment until diarrhea resolves to ≤ grade 1. • Restart with study treatment reduced by one dose level.⁴ • If 3 dose reductions of study treatment are clinically indicated, permanently discontinue study treatment.

1. Uncomplicated diarrhea defined by the absence of symptoms such as cramping, nausea/vomiting, ≥ grade 2, decreased performance status, pyrexia, sepsis, neutropenia ≥ grade 3, frank bleeding, and/or dehydration requiring intravenous fluid substitution.
 
2. Complicated diarrhea defined by the presence of symptoms such as cramping, nausea/vomiting, ≥ grade 2, decreased performance status, pyrexia, sepsis, neutropenia ≥ grade 3, frank bleeding, and/or dehydration requiring intravenous fluid substitution.
 
3. Loperamide should be made available prior to start of study treatment so loperamide administration can begin at the first signs of diarrhea.
 
4. Escalation of study treatment to previous dose level is allowed after consultation with the medical monitor and in the absence of another episode of complicated or severe diarrhea in the 4 weeks subsequent to dose reduction.
		

6.2.11 Dabrafenib +/- Trametinib Dose Modification for **Vision Changes**

Episodes of vision changes have been observed in patients

CONFIDENTIAL

This document is confidential. Do not disclose or use except as authorized.

receiving dabrafenib, trametinib, or the combination of both therapies and can be caused by central serous retinopathy (CSR) with retinal pigment epithelial detachments (RPED), or Retinal Vein Occlusion (RVO). Patients are required to have a standard ophthalmic exam performed by an ophthalmologist at baseline, within 1 week prior to doing on week 9, and any time patients report visual disturbance. For Grade 2 visual changes or greater, this exam must occur within 24 hours of onset (or study team knowledge of the event). The exam will include indirect fundoscopic examination, visual acuity (corrected), visual field examination, tonometry, and direct fundoscopy. Special attention should be given to retinal (e.g., CSR, RPED) or retinal vein abnormalities (e.g., RVO).

Guidelines regarding event management and dose reduction for visual changes considered to be related to study treatment are provided in the table below.

Table 6-10: Dabrafenib +/-or Trametinib Treatment Modification Requirement for Vision Changes

CTCAE Grade	Management	Action and Dose Modification

Grade 1 Asymptomatic or symptomatic but not limiting ADL; intervention not indicated.
	
 • Consult ophthalmologist any time when patient reports visual disturbance. If there is visual loss or significant visual changes, consult ophthalmologist immediately (within 24 hours of study team awareness) • Workup to rule out CSR, RPED or RVO. Consult retinal specialist in case of CSR or RVO. • Report CSR and RVO as SAE. • Continue follow up examination(s) (by retinal specialist if available) for CSR, RPED and RVO. 	
 • Continue study treatment at the same dose level until ophthalmologic examination can be conducted.* • If ophthalmologic examination cannot be performed within 7 days of onset, interrupt study treatment until CSR and RVO can be excluded and symptoms resolve. • If CSR and RVO excluded, restart study treatment at same dose level. • If CSR: Interrupt study treatment until symptoms resolve and exam by retinal specialist shows resolution. May restart study treatment with one dose level reduction of trametinib. • If RVO: Permanently discontinue trametinib.

CONFIDENTIAL

This document is confidential. Do not disclose or use except as authorized.

Table 6-10: Dabrafenib +/- Trametinib Treatment Modification Requirement for Vision Changes

CTCAE Grade	Management	Action and Dose Modification

Grade 2 and Grade 3 Grade 2 defined as: Symptomatic with moderate decrease in visual acuity (20/40 or better); limiting instrumental ADL; local or non-invasive intervention indicated.
 
Grade 3 defined as: Symptomatic with marked decrease in visual acuity or marked visual field defect (worse than 20/40 but better than 20/200); severe pain or medically significant; operative intervention indicated.
	
 • Consult ophthalmologist immediately (within 24 hours of study team awareness). • Workup to rule out CSR, RPED or RVO. Consult retinal specialist in case of CSR or RVO. • Report CSR and RVO as SAE. • Continue follow up examination(s) (by retinal specialist if available) for CSR, RPED and RVO. 	
 • Interrupt study treatment until signs and symptoms have resolved to baseline. • If CSR and RVO excluded and symptoms resolved to baseline, restart study treatment reduced by one dose level. • If CSR: Interrupt study treatment until symptoms resolve and exam by retinal specialist shows resolution. If CSR resolves restart study treatment with trametinib dose reduced by one dose level. • If RVO: Permanently discontinue trametinib.

Grade 4 Sight-threatening consequences; urgent intervention indicated; blindness (20/200 or worse).
	
 • Consult ophthalmologist immediately (within 24 hours of study team awareness). • Workup to rule out CSR, RPED or RVO. Consult retinal specialist in case of CSR or RVO. • Report CSR and RVO as SAE. • Continue follow up examination(s) (by retinal specialist if available) for CSR, RPED and RVO. 	
Permanently discontinue study treatment.

Abbreviations: CSR = central serous retinopathy; RVO = retinal vein occlusion; SAE = serious adverse event * If visual changes are clearly unrelated to study treatment (e.g., allergic conjunctivitis), monitor closely but ophthalmic examination is not required. **If ocular toxicities do not resolve within 21 days, permanently discontinue trametinib.
		

6.2.12 Dabrafenib +/- Trametinib Dose Modification for **Pneumonitis**

Pneumonitis has been observed in patients receiving trametinib. To reduce the risk of pneumonitis, patients will be monitored closely for symptoms, evaluated with imaging and functional tests when appropriate.

Table 6-11: Dabrafenib + Trametinib Treatment Modification Requirements for Pneumonitis

CTCAE Grade	Management	Action and Dose Modification
Grade 1	
 • CT scan (high-resolution with lung windows) recommended. • Clinical evaluation and laboratory work-up for infection. • Monitoring of oxygenation via pulse-oximetry recommended. • Consultation with pulmonologist recommended. 	Continue study treatment at current dose.
Grade 2	
 • CT scan (high-resolution with lung windows). • Clinical evaluation and laboratory work-up for infection. • Consult pulmonologist. • Pulmonary function tests: If < normal, repeat every 8 weeks until ≥ normal. • Symptomatic therapy including corticosteroids if clinically indicated. 	
 • Interrupt study treatment until recovery to grade ≤1. • Restart with study treatment reduced by one dose level. • Escalation to previous dose level after 4 weeks and consultation with the overall PI may be considered. • If no recovery to grade ≤1 within 4 weeks, permanently discontinue study treatment.
Grade 3	
 • CT scan (high-resolution with lung windows). • Clinical evaluation and laboratory work-up for infection. • Consult pulmonologist. • Pulmonary function tests: If < normal, repeat every 8 weeks until ≥ normal. • Bronchoscopy with biopsy and/or BAL if possible. • Symptomatic therapy including corticosteroids as clinically indicated. 	
 • Interrupt study treatment until recovery to grade ≤1. • After consultation with the overall PI, study treatment may be restarted reduced by one dose level. • If no recovery to grade ≤1 within 4 weeks, permanently discontinue study treatment.
Grade 4	Same as Grade 3.	Permanently discontinue study treatment.

6.2.13 Dabrafenib +/- Trametinib Dose Modification for **Liver Chemistry Changes**

Table 6-12: Dabrafenib +/- Trametinib Dose Modification Requirements for Liver Chemistry Changes

Stopping Criteria and Action

CONFIDENTIAL

This document is confidential. Do not disclose or use except as authorized.

Table 6-12: Dabrafenib +/- Trametinib Dose Modification Requirements for Liver Chemistry Changes

Stopping Criteria and Action

Liver chemistry stopping criteria are defined as follows. When any of the liver chemistry stopping criteria are met, immediately discontinue study treatment, perform liver event follow-up assessments, and monitor the patient until liver chemistries resolve, stabilize, or return to baseline values.
 
• ALT $\geq 3x$ ULN and bilirubin $\geq 2x$ ULN ($>35\%$ direct bilirubin) (or ALT $\geq 3x$ ULN and international normalized ratio [INR] >1.5, if INR measured). NOTE: If serum bilirubin fractionation is not immediately available, study treatment should be discontinued if ALT $\geq 3x$ ULN and bilirubin $\geq 2x$ ULN. Serum bilirubin fractionation should be performed if testing is available. If testing is unavailable, record presence of detectable urinary bilirubin on dipstick, indicating direct bilirubin elevations and suggesting liver injury.• ALT $\geq 8x$ ULN.• ALT $\geq 5x$ ULN but $<8x$ ULN persists for 2 weeks.• ALT $\geq 3x$ ULN if associated with the appearance or worsening of symptoms of hepatitis or hypersensitivity such as fatigue, nausea, vomiting, right upper quadrant pain or tenderness, fever, rash, or eosinophilia.• ALT $\geq 5x$ ULN but $<8x$ ULN and cannot be monitored weekly for >2 weeks.

CONFIDENTIAL

This document is confidential. Do not disclose or use except as authorized.

7. ADVERSE EVENTS: LIST AND REPORTING REQUIREMENTS

An adverse event is any untoward medical occurrence associated with the use of the study drug(s), whether or not considered drug related. An adverse event (AE) can therefore be any unfavorable and unintended sign (including an abnormal laboratory finding, for example), symptom, or disease temporally associated with the use of a medicinal product, whether or not considered related to the study drug(s).

7.1 Expedited Adverse Event Reporting to the Overall PI and Merck

Investigators **must** report to the DF/HCC Overall Principal Investigator (PI) any serious adverse event (SAE) that occurs from the time of the first dose of study treatment up until 90 days after the last dose of study treatment. The report should be submitted on the MedWatch 3500A form.

A serious adverse event is any adverse event that is any of the following:

- Fatal (i.e., the adverse event actually causes or leads to death)
- Life threatening (i.e., the adverse event, in the view of the investigator, places the patient at immediate risk of death)
- Requires or prolongs inpatient hospitalization
- Results in persistent or significant disability/incapacity (i.e., the adverse event results in substantial disruption of the patient's ability to conduct normal life functions)
- A congenital anomaly/birth defect in a neonate/infant born to a mother exposed to the investigational product
- Considered a significant medical event by the investigator (e.g., may jeopardize the patient or may require medical/surgical intervention to prevent one of the outcomes listed above)
- Pyrexia accompanied by hypotension, dehydration, renal insufficiency and/or severe (grade ≥ 3) rigors/chills in the absence of an obvious infectious cause should be reported as an SAE.
- Occurrence of Cutaneous squamous cell carcinoma (SCC) must be reported as an SAE.
- Central serous retinopathy (CSR) and Retinal Vein Occlusion (RVO) must be reported as an SAE.

All adverse events that do not meet any of the criteria for serious should be regarded as **nonserious adverse events**

Investigators must report each serious adverse event to the Overall PI within 24 hours of learning of the occurrence. In the event that the participating investigator does not become aware of the serious adverse event immediately (e.g.,

CONFIDENTIAL

This document is confidential. Do not disclose or use except as authorized.

participant sought treatment elsewhere), the participating investigator is to report the event within 24 hours after learning of it and document the time of his or her first awareness of the adverse event. Report serious adverse events by telephone, email or facsimile using the MedWatch 3500A form to:

[name]
[contact]
Email: [contact]
[contact]

7.2 Expedited Reporting to the Food and Drug Administration (FDA)

The Overall PI, as study sponsor, will be responsible for all communications with the FDA. The Overall PI will report to the FDA, regardless of the site of occurrence, any serious adverse event that meets the FDA's criteria for expedited reporting following the reporting requirements and timelines set by the FDA.

The Overall PI must report to the FDA any suspected adverse reaction to study treatment (i.e., including active comparators) that is both serious and unexpected.

7.3 Expedited Reporting to Hospital Risk Management

Participating investigators will report to their local Risk Management office any participant safety reports or sentinel events that require reporting according to institutional policy.

CONFIDENTIAL

This document is confidential. Do not disclose or use except as authorized.

7.4 Routine Adverse Event Reporting

All Adverse Events **must** be reported in routine study data submissions to the Overall PI on the toxicity case report forms. **AEs reported through expedited processes (e.g., reported to the IRB, FDA, etc.) must also be reported in routine study data submissions.**

7.5 Monitoring of Adverse Events and Period of Observation

All adverse events, both serious and non-serious, and deaths that are experienced by participants will be collected from the time of the first dose of study treatment up until 90 days after the last dose study treatment, or until death if death occurs first. The presence and resolution of AEs and SAEs (with dates) should be documented on the appropriate case report form and recorded in the participant's medical record to facilitate source data verification.

For some SAEs, the Overall PI or designee may follow-up by telephone, fax, and/or monitoring visit to obtain additional case details deemed necessary to appropriately evaluate the SAE report (e.g., hospital discharge summary, consultant report, or autopsy report).

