3. PARTICIPANT SELECTION

3.1 Inclusion Criteria

- 3.1.1 Participants must have histologically confirmed metastatic or unresectable melanoma
- 3.1.2 Participants must have BRAFV600-mutation status known (molecularly confirmed using validated, commercially available assay performed in a CLIA-approved laboratory).
 - If test at CLIA-certified lab used a non-FDA approved method, information about the assay must be provided. (FDA approved tests for BRAF V600 mutations in melanoma include: THxID BRAF Detection Kit and Cobas 4800 BRAF V600 Mutation Test).
- 3.1.3 Participants must have measurable disease, defined as at least one lesion that can be accurately measured in at least one dimension (longest diameter to be recorded) as ≥ 20 mm with conventional techniques or as ≥ 10 mm with spiral CT scan. See section 11 for the evaluation of measureable disease.
- 3.1.4 Age greater than or equal to 18 years. Because no dosing or adverse event data are currently available on the use of the combination of trametinib with or without dabrafenib, and pembrolizumab in participants less than 18 years of age, children are excluded from this study.
- 3.1.5 ECOG performance status ≤ 1 (see Appendix A).
- 3.1.6 Life expectancy of greater than three months in the opinion of the investigator.

CONFIDENTIAL

This document is confidential. Do not disclose or use except as authorized.

3.1.7 Participants must have normal organ and marrow function as defined below:

- Leukocytes (WBC) $\geq 3,000/\mu\text{L}$
- Absolute neutrophil count $\geq 1,500/\mu\text{L}$
- Platelets $\geq 100,000/\mu\text{L}$
- total bilirubin $\leq 1.5 \times$ institutional upper limits of normal; total bilirubin $> 1.5 \times$ above institutional upper limits of normal will be allowed if direct bilirubin is within normal limits or if patients has a documented history of Gilbert's disease
- AST (SGOT)/ALT (SGPT) $\leq 2.5 \times$ institutional upper limit of normal
- Creatinine within normal institutional limits or creatinine clearance (eGFR) $\geq 60 \text{ mL/min/1.73 m}^2$ for subjects with creatinine levels about institutional normal.

CONFIDENTIAL

This document is confidential. Do not disclose or use except as authorized.

- 3.1.8 Participants must have disease amenable to and be willing to undergo serial core or excisional biopsies of a tumor lesion(s).

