5.6 Duration of Follow Up

If treatment is discontinued for completion of two years of pembrolizumab, or for disease progression, or for withdrawal of consent, participants will be followed for adverse events. All adverse events encountered from time of the first dose of study treatment up until 90 days after the last dose of study treatment will be followed until one of the following occurs:

- The event resolves,
- The participating investigator assesses the event as stable,
- The participating investigator determines the event to be irreversible,
- The participant is lost to follow-up,
- The participant dies.

If the subject is not seen in clinic after the off-study visit, required Adverse Event details must be collected over the phone.

CONFIDENTIAL

This document is confidential. Do not disclose or use except as authorized.

If treatment is discontinued for a reason other than disease progression, study discontinuation, or withdrawal of consent, participants will be seen every 12 weeks (+/- 2 weeks) for imaging until progressive disease or death, whichever comes first. If there are any adverse events that have not resolved, or been assessed by the participating investigator as stable or irreversible at the time of progressive disease, the participant will be followed until the adverse events resolve, or are assessed by the participating investigator as stable or irreversible.

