9. BIOMARKER, CORRELATIVE, AND SPECIAL STUDIES

9.1 Collection of Specimen(s)

Tumor biopsies are required be performed in all patients for both cohorts at four time points (as all patients are enrolled onto the first Stage of the Simon 2-stage design):

1. Prior to commencing MTT
2. Following 2-week MTT lead-in
3. Following 6-weeks of combined pembrolizumab with MTT (if feasible)
4. A biopsy at the time of disease progression will also be performed (this is optional)

Multiple cores will be obtained and/or sufficient tumor excised at each biopsy time-point, assuming that it is safe to do so (e.g. patients with rapid responses may have very little tumor to biopsy safely at the latter time points). Core biopsies or portions of the excised tumor will be processed with the following hierarchy in mind:

1. DNA/RNA/protein extraction ([name])
2. Disaggregation and flow cytometry ([name])
3. FFPE ([name])
4. Single-cell RNA seq of T cells ([name])
5. Single-cell RNA seq of tumor cells ([name])

Analysis will then be carried out to compare changes seen longitudinally and to determine if those changes are associated with improved outcomes to therapy with study treatment. Most of this work will be exploratory in nature, as analysis

CONFIDENTIAL

This document is confidential. Do not disclose or use except as authorized.

such as the technology for single-cell sequencing of tumor and T-cells is emerging and no data is presently available to inform how these analyses might be used to help predict which patients are most likely to benefit from single-agent or combination therapy. However, based on previous work, there are two assays that will be incorporated into a predictive model, PD-L1 expression by immunohistochemistry (IHC) and immuno-sequencing (immunoSEQ) using the Adaptive Biotechnologies platform.

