- f. Albumin, alkaline phosphatase, total bilirubin, BUN, creatinine, calcium, chloride, glucose, HCO₃, LDH, phosphorus, potassium, total protein, SGOT [AST], SGPT [ALT], sodium. TSH will be performed at baseline, week 3 and then every 6 weeks.
- g. Radiographic imaging will be performed within 4 weeks of lead-in therapy commencement, within 1 week prior to Week 9, every six weeks thereafter (within 1 week prior to W15, W21, W27) until week 27, and then every 12 weeks (+/- 2 weeks) through 48 weeks of pembrolizumab therapy. Additionally, following initial disease progression, if a participant is treated beyond progression, tumor assessments must be repeated ≥ 4 weeks after initial disease progression in order to confirm disease progression. The tumor assessment must not be repeated any sooner than 4 weeks after initial disease progression.
- h. Serum pregnancy test (women of childbearing potential).
- i. Ejection fraction measurement done at screening and within 1 week prior to dosing on week 9. The same modality (ECHO or MUGA) should be used at baseline and at follow-up; should be performed with increased frequency if clinically indicated.

CONFIDENTIAL

This document is confidential. Do not disclose or use except as authorized.

- j. Correlative blood analysis will be performed prior to MTT, prior to pembrolizumab therapy initiation, prior to every pembrolizumab dose through week 27, prior to every other pembrolizumab dose after week 27 (week 33, week 39, etc.), and at time of disease progression. BRAF samples will be collected in 1-10 mL green sodium heparin and 1-10 mL red top serum tubes
- k. Tumor biopsies and PBMC blood analysis will be performed pretreatment, prior to pembrolizumab therapy initiation (up to 5 days prior), at the conclusion of combined targeted therapy plus pembrolizumab therapy (up to 5 days prior), and then at the time of disease progression. PBMC samples will be collected in 2-8 mL blue tiger top CPT tubes.
- l. Pembrolizumab will be administered at a dose of 200 mg IV every three weeks.

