- m. Off-study evaluation visit is completed within 30 days after the last dose of study medication. If treatment is discontinued for a reason other than completion of two years of pembrolizumab, disease progression or withdrawal of consent, patients will be seen every 12 weeks (+/- 2 weeks) with imaging performed prior to these evaluations. If patients have an ongoing response or stable disease 18 months (+/- 2 months) after their last dose of pembrolizumab, patients will be followed every three-twelve months, based on investigator discretion, with imaging performed every 3-12 months.
- n. BSA should be calculated using the baseline height.
- o. Vitals signs include pulse, body temperature, blood pressure (BP), and respiratory rate. In subjects with an initial BP reading within the hypertensive range, a second reading should be taken at least 1 minute later per Section 6.2.8BRAD
- p. Adverse Event Reporting: All adverse events, both serious and non-serious, will be collected from the time of the first dose of study treatment up until 90 days after the last dose of study treatment, or until death if death occurs first. The adverse events are followed to their resolution, or until the participating investigator assesses them as stable, or the participating investigator determines the event to be irreversible, or the participant is lost to follow-up. If the subject is not seen in clinic after the off-study visit, required Adverse Event details must be collected over the phone.
- q. Rash prophylaxis is recommended for the first 6 weeks of study treatment. See Table 6-3.
- r. If treatment is discontinued for a reason other than disease progression, study discontinuation, or withdrawal of consent, participants will be seen every 12 weeks (+/- 2 weeks) for imaging until progressive disease or death, whichever comes first.

CONFIDENTIAL

This document is confidential. Do not disclose or use except as authorized.

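### Adverse event collection opens at the first dose, so complications of the required baseline research biopsy that start before dosing fall outside the trial's safety data

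*Combined protocol and SAP*

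**What the plan says.** Four places set the safety window, and all open it at the same point.

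- Section 7.5: all adverse events and deaths "will be collected from the time of the first dose of study treatment up until 90 days after the last dose study treatment".
- Section 7.1: investigators must report to the Overall PI, within 24 hours of learning of it, "any serious adverse event (SAE) that occurs from the time of the first dose of study treatment" until 90 days after the last dose.
- Section 5.6, on follow-up to resolution: "All adverse events encountered from time of the first dose of study treatment up until 90 days" after the last dose.
- Study calendar (section 10), note p: events "will be collected from the time of the first dose of study treatment up until 90 days after the last dose of study treatment".

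The biopsy schedule begins earlier. Section 9.1 states: "Tumor biopsies are required be performed in all patients for both cohorts at four time points". The first of the four comes before any targeted therapy (MTT). The labels for feasibility and optionality apply there only to the third and fourth time points. Calendar note k agrees: "Tumor biopsies and PBMC blood analysis will be performed pretreatment". Willingness to have serial core or excisional biopsies is an inclusion criterion (3.1.8). Baseline evaluations may take place up to 2 weeks before therapy starts (section 10).

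The analysis rules follow the same start. Section 13.6 limits the safety set to patients given at least one dose of the drug combination, and section 13.7.1 counts toxicity from first treatment.

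**The concern.** The baseline biopsy is an invasive procedure done because the protocol requires it, with multiple cores or excised tumor going to research assays. Bleeding, pneumothorax, infection or a hospital admission between that biopsy and the first dose is a harm of taking part in the trial, yet the routine window has not opened when it occurs.

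The definition of an adverse event at the start of section 7 does not help, because it refers to use of the study drug and does not mention protocol procedures. The monitoring committee in section 12.2 sees unexpected events that have been reported, so it depends on the same window. A patient whose complication prevents dosing altogether also leaves the data set: section 4.1 cancels the registration of anyone who receives no protocol therapy. At stake is a safety account that can understate the risk of participation for the one baseline procedure most likely to cause harm. The efficacy design is not affected.

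**Working it through.** The point rests on the text, so the first step is to set the rules beside the timing of the biopsy. The second step only gives a sense of scale.

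**Step 1. What each rule does with a baseline-biopsy complication**

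| Rule | Onset before first dose | Onset after first dose |
|---|---|---|
| Adverse event collection (7.5, note p) | outside | inside |
| 24-hour SAE report (7.1) | outside | inside |
| Follow-up to resolution (5.6) | outside | inside |
| Safety tables (13.6), toxicity evaluability (13.7.1) | outside | inside, once the dosing requirement for the set is met |
| Registered but never dosed (4.1) | registration cancelled | does not arise |

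Biopsies after the lead-in and after induction are taken when treatment has already begun, so their complications are inside the window. The optional biopsy at progression is inside it too while the patient is on treatment or within 90 days of the last dose.

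One detail shows how narrow the gap is. Section 5.4.1 already records concomitant medication from 28 days before the first dose. An antibiotic given for a biopsy infection in that period would be on the case report form, while the infection would not.

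**Step 2. Scale**

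Inputs:

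- Number of patients with a baseline biopsy. The lowest case is n = 14: one cohort stopping at its first stage, since section 2.3 opens cohort 1 first and only considers cohort 2. The middle case is n = 28: both first stages, 2 × 14. The upper case is n = 50: both cohorts complete (section 13.2).
- Who must be biopsied. Sections 1.1, 2.4 and 5.1 tie biopsies to first-stage patients, while section 9.1 says all patients. On either reading the baseline biopsy is required for the 14 first-stage patients in a cohort.
- Complication rate p. The documents give none. The range 1% to 5% is an assumption.
- Onset. All complications are taken to start before the first dose, which makes the results upper figures for a given n and p.

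Formula: P(at least one event) = 1 − (1 − p)^n.

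Table 13.1 uses this formula with n = 28. It reproduces at all seven incidences: 0.245, 0.574, 0.762, 0.903, 0.929, 0.948 and 0.989, against the printed 0.25, 0.57, 0.76, 0.90, 0.93, 0.95 and 0.99.

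Applied to the baseline biopsy:

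| n | p = 1% | p = 5% | Expected events, n × p |
|---|---|---|---|
| 14 | 1 − 0.99^14 = 0.13 | 1 − 0.95^14 = 0.51 | 0.14 to 0.70 |
| 28 | 1 − 0.99^28 = 0.25 | 1 − 0.95^28 = 0.76 | 0.28 to 1.40 |
| 50 | 1 − 0.99^50 = 0.39 | 1 − 0.95^50 = 0.92 | 0.50 to 2.50 |

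The counts of 14 and 25 per cohort are patients evaluable for the primary endpoint, so the number actually biopsied could be somewhat higher.

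**The case against.** The sponsor can fairly reply that the window is a deliberate choice, stated the same way four times, and that serious events before dosing would still come to light.

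- Section 4.1 asks that issues that would delay treatment be discussed with the Overall PI.
- Section 5.7 requires immediate notice to the Principal Investigator of unusual or life-threatening complications, with no first-dose limit.
- Section 7.3 sends sentinel events to local Risk Management under institutional policy, again with no such limit.
- Section 7.4 adds that events reported through expedited processes must also enter routine data submissions.

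These routes are real, and they rule out some stronger readings. A reader might infer that biopsy complications are neither collected nor reported at all. The documents do not support that: only pre-dose complications of the first biopsy are outside the window, and part of those may be notified. A reader might also infer that a complication which merely delays dosing cancels the registration. Section 4.1 does not say so; cancellation applies only if no protocol therapy is received. Nor can it be said that the Overall PI or the IRB would be unaware of every such event.

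What remains is that none of these routes is systematic adverse event collection. A discussion of a delay or a notice to Risk Management creates no entry in the trial's adverse event data. Section 7.4 carries forward only what was already reported, and the section 13.6 safety set still excludes a patient who is never dosed.

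One further limit: some text after the SAE rule in section 7.1, whose title also names the drug supplier, is missing from the public copy. A rule for events before dosing could stand there. If it does, it needs to be reconciled with the four windows.

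**Conclusion.** The point holds in a limited form. Following the visible text exactly, complications of the required baseline biopsy with onset before the first dose are outside routine adverse event collection, the 24-hour SAE rule and the section 13.6 tables. A patient harmed enough never to be dosed leaves the data set as well.

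That conclusion follows from the text and holds whatever the complication rate. The size does not: the 13% to 92% span from the smallest to the largest case rests on an assumed 1% to 5% rate, on onset before the first dose, and on how many patients are biopsied. It should be read as scale only. Because part of section 7.1 is missing and partial notification routes exist, confidence is moderate rather than high. The change is worth making because it is cheap and concerns harm from a research procedure. Sample size, type I error and power are unaffected.

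**What to change.** - In sections 5.6, 7.1 and 7.5 and calendar note p, start collection and expedited reporting at consent, or at the first protocol-mandated procedure, for events attributable to a protocol procedure. Keep the first dose as the start for all other events.
- Extend the adverse event definition in section 7 so that procedure-related events count, and bring section 13.7.1 into line.
- In section 13.6, add a listing of procedure-related events for every participant who had a biopsy, including those never dosed and those whose registration was cancelled.

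The cost is protocol wording, one attribution field on the case report form and slightly more adverse event entry. No new visits or procedures are needed.
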